8.2 Stratification Factors

25 patients will be recruited to Oncolo-GIST trained clinicians, and 25 patients will be recruited to usual care clinicians in Phase 2.

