Study Population:	Phase 1 Interviews: Bereaved Caregiver subjects will be caregivers of patients who died in the past year with a primary diagnoses of GI or lung cancers. Clinician subjects will be either oncologists, palliative care physicians, nurses, nurse practitioners, social workers and psychologists who care for patients with metastatic GI and lung cancers. Phase 2: Patient subjects will be adults (18+) diagnosed with lung, head and neck, or GI cancer, with a progression of their disease after one line of therapy. Clinician subjects will be Lung, Head and Neck, or GI oncologists. All subjects' primary language will be English and will have full mental capacity.
Enrollment Period:	Phase 1 (Interviews): 12 months Phase 2: 19 Months
Study Design:	Phase 1 (Interviews): Intervention manual development Phase 2: Intervention phase (two-group pilot randomized trial).
Participants:	Participants will be recruited at Weill Cornell Medical College/ New-York Presbyterian Hospital, at the Lung and GI Cancer centers.
Study Duration:	31 months Start date: Jan 22, 2020 End date: July 25, 2022 (end enrollment); January 25 th , 2023 (end data analysis and all other activities)
Participant Duration:	Phase 1 Interviews: 2 hours Phase 2: 4 months (with patient status monitoring up to 12 months)
Primary Objective:	To assess the effectiveness of the Oncologist intervention by examining the patient's degree of prognostic understanding after discussing

prognosis with either Oncolo-GIST trained or non-Oncolo-GIST trained clinicians.

Secondary Objectives:

To examine the effects on patients of having better prognostic understanding, including its effect on their quality of life, the type of care they choose to receive and whether or not the care they received was consistent with the patient's preferences and values.

Endpoints:

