In Phase 2, for the pilot cluster RCT study (Aim #3), we will recruit adult patients (n=50) with metastatic GI, head and neck, or lung cancers with scan results that reveal progression (worsened disease) on an initial systemic treatment; that is, patients whose life-expectancy can reliably be estimated to be months, not years.^{5 9} Medical oncologists (n=4) who care for these patients will also be consented for study participation and half (n=2) will be randomized to receive the brief "Oncolo-GIST communication" training. The Oncolo-GIST training will provide instruction in how to introduce the topic of prognosis, describe scan results as "worse," prognosis as "likely months, not years," and expected treatment outcomes (e.g., "not expected to be cured by treatment," and expected impact on quality of life – that is, whether the anticancer treatment is likely to make them feel overall better or worse). We expect 12-13 patients will be clustered within each of the 4 oncologists. Hierarchical Linear Modeling (HLM) techniques will be employed to address the non-independence of patient assessments within each cluster. Patients (n=25) will be seen by either an Oncolo-GIST trained oncologist or an oncologist not trained in the intervention; that is, usual care (n=25). Patients in both arms will have met the same eligibility criteria (i.e., have similar prognoses).

Thus, we will get initial feedback on the Oncolo-GIST intervention from relevant stakeholders and key informants, obtain information on the patient and oncologist experience with the intervention and evaluate its feasibility and acceptability. Finally, we will obtain preliminary effect size estimates

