on the Oncolo-GIST Version 2.0's effect on our primary outcome – patient prognostic understanding – to inform the planning of a future larger scale efficacy randomized controlled trial (RCT). Patients will be assessed by trained research staff in the week prior to a scheduled meeting with their oncologist to discuss the scan results. This will provide patients' baseline levels of prognostic understanding and enable us to determine how the intervention relates to pre-post scan visit changes in prognostic understanding. Although the first scheduled scan after study enrollment may not reveal progressive disease, we have been assured by Drs. [name] and [name] that only exceptional cancer patients will not progress within 12 months of baseline. We thus propose to follow patients for 12 months or until a progression is detected in the scan, whichever comes first.

Patients will be assessed pre-scan, post-scan within a week of that progressive scan visit and after their two next scans, if applicable. [see Human Subjects section for Study Timeline & Assessment Schedule and details of assessment procedures]. Although not all patients are expected to die within the study observation period, given a median life expectancy of ~4-5 months from baseline,⁹ we expect nearly half of the enrolled patients will die 4 months from baseline, and that the vast majority will die during the study observation period. Thus, for all patients enrolled in this study, the medical care that they receive can reasonably be considered end-of-life care, whether they die during the study observation period or not.

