3.2 Interviews, Focus Groups, Surveys, and/or Observations

A. Administration

▪ Timing and Frequency

Phase 1 Interviews: Clinicians and bereaved caregivers will complete a one-time, 2 hour phone study session or REDCap survey (including embedded intervention manual) link.

Phase 2: Patients will be assessed in the week prior to their scheduled scan, within 1 week of the clinic visit in which progressive scan results are discussed, and then after their next two scans, if they have them, to explore intervention effects on primary and secondary outcomes, respectively. Oncologists will be assessed in the week following that same clinic visit to obtain their impressions of the discussion of prognosis and the patient's prognostic understanding. All these assessments will take 20-30 minutes.

Trained oncologists will complete a brief (5-minute) post-training quiz, and all oncologists will complete a brief (5-minute) survey on Oncolo-GIST at the end of the

study. Additionally, patients will be monitored via EPIC for progression of disease up to 12 months.

- *Location*

Phase 1 interviews of caregivers and clinicians will take place at a location convenient to the participant over the phone or via REDCap. Assessments of patients and clinicians in the pilot stage will take place in-person in clinic, at a time convenient for the participant at a different appointment, or over the telephone. Patients in Phase 2 will also have the option of completing the surveys themselves via a secure web link if this is more convenient to them.

- *Person Identifiers*

Co-investigators may review EPIC to identify potential participants who meet eligibility. Contact information and appointment information will also be collected for either in-person or letter (postal and email) recruitment. Only data from potential participants will be stored on secure servers. Patient subjects will also have data collected via medical chart abstraction including diagnoses, medications, advanced directives, and types of care received (e.g. hospice). These data will be deleted upon completion of the study.

B. Study Instruments

- Phase 1 Interviews for both clinician and bereaved caregiver subjects will consist of a survey including demographics and oncology based communication questions specific to either the clinicians or caregivers. After each section of the Oncolo-GIST manual, participants will answer open-ended questions about the module they just reviewed.

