4.2 Inclusion Criteria

Phase 1 Interviews:

Bereaved Caregivers:

1. Caregivers of patients who died in the past year with a primary diagnoses of GI or lung cancer
2. Fluent in English

Clinicians:

1. Currently care for patients with metastatic GI and lung cancers as an oncologist, palliative care physician, nurse, nurse practitioner, social worker, or psychologist

Phase 2:

Patients:

1. Male or female \geq 18 years of age.
2. Receiving ongoing care (\geq 2 visits) that includes regular scans
3. Progression on at least 1 line of systemic cancer therapy
4. Prognosis from an oncologist of less than 12 months
5. Receiving care from an oncologist participating in the Oncolo-GIST study
6. Fluent in English

Clinicians:

1. Specialize in Lung, Head and Neck, and GI cancers
2. Currently provide care at the WCM Lung, Head and Neck, and GI cancer clinics
3. Fluent in English

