6.1 Schedule of Assessments

Table 1. Schedule of trial events for Phase 1 Interviews (Bereaved Caregivers and Clinicians)

	Pre-study	Visit 1 (Interview)
Screening	X	
Informed Consent (see note)	X	
Review of Oncolo-GIST intervention		X
Demographics		X
Oncology Based Communication Questions		X
Semi-structured Interview		X

Table 2. Schedule of trial events for Phase 2

	Arm	Pre-Study	Pre-Scan	Post-Scan 1 (approx. 1 week)	Post-Scan 2	Post-Scan 3	Post-Scan 4 (up to 12 months)
Short Portable Mental Status Questionnaire ^s	P	X					
Health Literacy Assessment (REALM) ^s	P	X					
Informed Consent	B	X					
Oncolo-GIST Training (Clinicians)	C*	X					
Demographics	P		X				
4 Item Illness Understanding	P		X				
Treatment Intent	P		X				
Treatment Preferences	P		X				
CWC II Psychological questions	P		X				
NCCN Distress Thermometer	P		X				
The Human Connection Scale	P		X	X	X	X	
HADS	P		X	X	X	X	
McGill Quality of Life Questionnaire	P		X	X	X	X	
PSWQ-Ultra Brief	P		X				
PANAS	P		X				
Primary Appraisal Secondary Appraisal (PASA) items (Threat and Challenge subscales only)	P		X				
Post Scan Clinician Questionnaire	C			X			
Medical Chart Abstraction	C				X	X	X
Post Scan Patient Questionnaire	P			X	X	X	
Training Quiz	C*	X					
Post-Study Questionnaire	C						X

C = Clinicians, P = Patients, B = Both, ^s= Screening, * = Intervention Arm Only

Note: The Post-Scan 4 Chart Abstraction will occur when monitoring if progression of the disease is found after Post-Scan 3 or the patient is deceased; up to 12 months.

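### Four oncologists from up to three specialties are randomised 2:2 with no stratification factor named; if they form two same-specialty pairs, pairing would remove an avoidable chance imbalance (minor)

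*Combined protocol and SAP*

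**What the plan says.** Section 3.1 describes Phase 2 as a pilot cluster trial in which, of four medical oncologists, "half (n=2) will be randomized to receive the brief" Oncolo-GIST training. Section 8.1 repeats the split of two trained and two usual care, with 50 patients.

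On specialty, the Protocol Summary and section 4.1 say "Clinician subjects will be Lung, Head and Neck, or GI oncologists". The clinician inclusion criterion in section 4.2 reads "Specialize in Lung, Head and Neck, and GI cancers", with *and* where the other two places have *or*. Nowhere is it stated how many of the four come from each specialty, or whether each treats one cancer type only.

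Section 8.2 is headed Stratification Factors. Its whole content is "25 patients will be recruited to Oncolo-GIST trained clinicians, and 25 patients will be recruited to usual care clinicians in Phase 2". That is a patient count per arm, not a factor. No section describes an allocation method, pairing or any other restriction.

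Section 8.3.1 plans a hierarchical linear model (HLM) with oncologist as a random effect and baseline covariates, of which health literacy is the only example. Its stated product is a preliminary effect size for planning a larger trial.

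**The concern.** With four randomised units, one draw settles which specialties sit in which arm. If that draw puts all of one specialty in the trained arm and all of another in usual care, the arm comparison is also a specialty comparison. If each oncologist treats one cancer type, cancer type is then constant within oncologist and aligned with arm, so adjustment cannot recover the training effect. The effect size carried into planning the larger trial would contain any difference between specialties in how patients' prognostic understanding changes. A restriction on the allocation can prevent this beforehand; no analysis can repair it afterwards.

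**Working it through.** The documents give no figure for this risk, so there is none to reproduce. The stated cluster size is consistent: 50/4 = 12.5, against 12–13 per oncologist in section 3.1.

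**Inputs.** Four oncologists, 2:2 (sections 3.1 and 8.1); up to three specialties (Protocol Summary, section 4.1). *Assumptions:* simple allocation, so C(4,2) = 6 equally likely draws; one cancer type per oncologist.

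**1. Draws in which the arms share no specialty**

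| Specialty mix | Simple 2:2 | Same-specialty oncologists paired |
|---|---|---|
| 2-2 | 2/6 | 0/4 |
| 2-1-1 | 2/6 | 0/4 |
| 3-1 | 0/6 | 0/4 |
| 4-0 | 0/6 | 0/4 |

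Zero does not mean balance in a 3-1 mix: one arm always holds the only oncologist of the second specialty.

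**2. Size of the shift, 2-2 mix.** Let the oncologist means be 0, 0, D, D, apart from any training effect.
- Separated draws (2 of 6): the arm means differ by D. Each arm holds two equal oncologists, so the within-arm variance from specialty is 0. On the four clusters, the columns for intercept, arm and specialty have rank 2, not 3, so the arm effect is not estimable after specialty adjustment.
- Mixed draws (4 of 6): both arm means are D/2, so the shift is 0. The within-arm variance is 2 × (D/2)² / (2 − 1) = D²/2.
- Mean squared shift over the six draws: (2/6) × D² = D²/3.
- With two oncologists per arm, the variance of the arm difference is s² × (1/2 + 1/2) = s², where s² is the within-arm oncologist variance. Its mean over the six draws is (4/6) × D²/2 = D²/3, equal to the mean squared shift.
- With pairing, the shift is 0 in all four draws, while s² still contains D²/2. An HLM without a pair term therefore gives an interval that is conservative for specialty.

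**3. The 2-1-1 mix.** Let two oncologists have mean G and the others L and H. The separated draws shift the arm difference by G − (L + H)/2. The other four, which are the only draws under pairing, shift it by (L − H)/2 in size.
- G = 0, L = a, H = −a: the separated shift is 0 and the other shift is a. The mean squared shift is (4/6)a² = 0.67a² unpaired and 1.00a² paired. Under pairing the within-arm variance is a²/2 = 0.50a², so the interval is anti-conservative for specialty.
- G = 0, L = H = a: the separated shift is a and the other shift is 0. The mean squared shift is (2/6)a² = 0.33a² unpaired and 0 paired.

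Pairing helps here only if G lies outside the range from L to H. The documents do not say whether it does.

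**4. Scale.** With 25 patients per arm and 4 − 2 = 2 cluster-level degrees of freedom, the 95% half-width of the arm effect, before baseline adjustment, is t(0.975, 2) × √((2/25)(1 + 11.5 × ICC)), in SD units:
- ICC 0: 4.303 × 0.283 = 1.22 SD.
- ICC 0.05: 4.303 × 0.355 = 1.53 SD.

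The ICC values are assumptions; the documents give none.

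**The case against.** **The conditions are not documented.** Harm needs simple allocation, a 2-2 or 2-1-1 mix, one cancer type per oncologist, and a specialty difference in the outcome. None is established. Section 4.2, read literally, has every oncologist covering all three cancers, and the risk would then be nil. This stands, and it is why the point is conditional. Section 4.4 does draw patients from GI, head and neck, and lung clinics, so a mixed set of oncologists is plausible.

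**The plan already narrows the gap.** Section 3.1 says "Patients in both arms will have met the same eligibility criteria (i.e., have similar prognoses", and the baseline assessment is meant to "enable us to determine how the intervention relates to pre-post scan visit changes in prognostic understanding". Common eligibility narrows one route to a specialty gap, and change scores remove stable differences in level. Neither removes a specialty difference in change, but D may be small.

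**The model already carries the risk.** A reader might infer that the HLM is blind to specialty imbalance, or that the trial is biased by design. The documents do not support either. Over the six draws the estimated variance averages D²/3, which matches the mean squared shift. Only within a separated 2-2 draw does the within-arm variance fail to show the gap. Cancer type by arm can also be tabulated, since patients will have "data collected via medical chart abstraction including diagnoses, medications, advanced directives, and types of care received".

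**Specialty is one trait among several.** A trait that splits both pairs, such as seniority, separates fully in 2/4 paired draws against 2/6 unpaired. The documents do not rank specialty above such traits. This stands as a cost of pairing.

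**Conclusion.** The point holds as a minor, conditional improvement. For a 2-2 mix, under simple allocation and one cancer type per oncologist, there is a 2/6 chance that arm and specialty are fully confounded. Same-specialty pairing takes this to 0/4 and the mean squared specialty shift from D²/3 to 0. The practical gain depends on D, which the documents do not give.

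A reader might go further and ask for pairing whatever the mix. The arithmetic does not support that: in a 2-1-1 mix pairing removes the no-overlap draws but can raise the error, and for 3-1 and 4-0 there is no no-overlap risk to remove.

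The main limit on the estimate is the four clusters, with a half-width of 1.22 to 1.53 SD over the assumed ICC range. Pairing does not change that.

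**What to change.** In section 8.2, state the allocation method, the specialty of each of the four oncologists, and whether each treats one cancer type. If they form two same-specialty pairs, randomise one of each pair to training. Do not prescribe pairing for a 2-1-1 mix.

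Keep the section 8.3.1 HLM with oncologist as a random effect and no pair or specialty term. In a 2-2 mix such a term would leave 1 cluster-level degree of freedom instead of 2.

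In every case, report cancer type by arm. If allocation has already been made and the arms share no specialty, say in the report that the estimate cannot be separated from specialty.

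The cost is two or three sentences and one descriptive table. Both members of a pair must consent before allocation. The possible allocations fall from 6 to 4, so the smallest two-sided randomisation p-value goes from 2/6 = 0.33 to 2/4 = 0.50. Neither can reach 0.05, so no usable test is lost. A trait that splits both pairs becomes more likely to separate the arms, as noted above.

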8.3 Analysis of Endpoints

8.3.1 Analysis of Primary Endpoints

Phase 1 Interviews: We will obtain feedback on the current version of Oncolo-GIST (Version 1.0). Morse’s guidelines¹⁵ for rigorous qualitative research (e.g., audit trail, saturation) will be followed and Atlas.ti software used.¹⁶ Themes emerging will be quantified (re: frequency, priority) and considered to inform revisions to the Phase 1 Open Trial Oncolo-GIST intervention.

Phase 2: We will generate preliminary effect size estimates to inform the planning of the larger, efficacy randomized controlled trial (RCT). Hierarchical Linear Modeling (HLM)¹⁷ will be used to evaluate intervention effects. HLM is statistically appropriate because it accounts for the clustering of patients within oncologists, creating nonindependence of clustered assessments. HLM will model oncologists as a random effect as has been done in prior RCTs.^{18 19} Baseline covariates known to affect study outcomes (e.g., patient health literacy) will be included in models to increase the precision of effect size estimates.²⁰ This will provide a preliminary effect size estimate of Oncolo-GIST Version 2.0’s ability to improve patients’ prognostic understanding for a future, larger study. Linear and logistic regression models will estimate effects of the

Oncolo-GIST intervention on secondary and exploratory outcomes.

9. Adverse Event Reporting Requirements

Adverse event (AE) monitoring and reporting is a routine part of clinical research. Safety is monitored by evaluation of adverse events reported by subjects or observed by investigators or research staff, as well as by other investigations such as clinical laboratory tests, x-rays, electrocardiographs, etc.

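### Section 8.3.1 gives secondary and exploratory outcomes plain linear and logistic regression although oncologists, two per arm, are randomised; as written, the intervals are too narrow unless the ICC is negligible

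*Combined protocol and SAP*

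**What the plan says.** Section 3.1 makes the oncologist the randomised unit: of four, "half (n=2) will be randomized to receive the brief" training. It expects 12-13 patients per oncologist, and Section 8.1 repeats the split of two oncologists and 25 patients per arm. Section 3.1 also says in general terms, naming no outcome, that "Hierarchical Linear Modeling (HLM) techniques will be employed to address the non-independence of patient assessments within each cluster".

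Section 8.3.1 justifies the hierarchical model because "it accounts for the clustering of patients within oncologists, creating nonindependence of clustered assessments", and adds that "HLM will model oncologists as a random effect as has been done in prior RCTs". It plans baseline adjustment: "Baseline covariates known to affect study outcomes (e.g., patient health literacy) will be included in models". It then describes the resulting estimate as the effect on prognostic understanding.

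The section's last sentence turns to the remaining outcomes and names another method. It begins "Linear and logistic regression models will estimate effects of the" and ends "Oncolo-GIST intervention on secondary and exploratory outcomes". It mentions no oncologist effect, cluster-robust variance or small-sample correction.

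The outcomes concerned include DNR completion, quality of life and type of care (Section 1, Endpoints). Objective 3 in Section 1.1.1 places type of care, quality of life and value-consistent care within the preliminary efficacy test.

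**The concern.** Patients of one oncologist share that oncologist's habits in discussing DNR orders, choosing further treatment and referring to palliative care. Only four such sets of habits are randomised. A single-level regression takes its standard error from the spread among patients, so a chance difference between two pairs of oncologists can look like a fairly precise intervention effect.

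The plan recognises this for prognostic understanding and then, on its face, drops the safeguard for the other outcomes. Section 8.3.1 opens with "We will generate preliminary effect size estimates to inform the planning of the larger, efficacy randomized controlled trial", so readers may carry the secondary estimates and their intervals forward. No test or decision rule is stated for these outcomes. What is at stake is therefore the honesty of the reported uncertainty, not a wrong decision by the trial.

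**Working it through.** The plan gives no figure for the precision of the secondary outcomes. Its power statement in Section 8.1 concerns prognostic understanding and is not used here.

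**Inputs.** Four oncologists, two per arm, and 12-13 patients each (Sections 3.1 and 8.1), taken as 13 and 12 in each arm, N = 50. The ICC is not in the documents; 0.01, 0.05, 0.10 and 0.20 are assumed. The interval level is assumed to be 95%, two-sided.

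**Design effect.** Σm²/N = (13² + 12² + 13² + 12²)/50 = 626/50 = 12.52, so the design effect is 1 + (12.52 − 1) × ICC = 1 + 11.52 × ICC. Its square root is the factor by which the true standard error exceeds the one that assumes independence.

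**Simulated coverage of a nominal 95% interval.** Linear case: 200,000 replicates, normal oncologist intercept, no true effect; pooled t on 48 df against oncologist-level means on 2 df (critical value 4.303). Logistic case: 400,000 replicates, beta-binomial outcome, Wald interval for the log odds ratio.

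| | ICC 0.01 | 0.05 | 0.10 | 0.20 |
|---|---|---|---|---|
| Design effect | 1.115 | 1.576 | 2.152 | 3.304 |
| Square root | 1.056 | 1.255 | 1.467 | 1.818 |
| Linear, single-level | 93.6% | 88.0% | 81.3% | 69.9% |
| Linear, one covariate (assumed correlation 0.4) | 93.5% | 86.7% | 79.4% | 67.6% |
| Logistic, 50% event rate | 94.2% | 88.4% | 81.5% | 70.2% |
| Logistic, 30% event rate | 94.1% | 88.8% | 82.6% | 72.8% |
| Half-width, single-level linear (SD) | 0.564 | 0.559 | 0.552 | 0.537 |
| Half-width, oncologist-level, 2 df (SD) | 1.14 | 1.36 | 1.58 | 1.96 |

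The single-level half-width shrinks as the ICC rises, because the within-arm variance misses part of the variation between oncologists. The error therefore grows slightly faster than the design effect alone implies.

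**When it does not matter.** At ICC 0 the single-level linear interval is correct. The logistic interval is not too narrow below an ICC of about 0.003 (coverage 95.2% and 95.1% at 0.002; 94.8% for both event rates at 0.005).

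**Oncologist-level comparison on 2 df.** Coverage across the four ICCs is 94.9-95.1% for means, with or without covariate adjustment, 94.0-94.8% for proportions and 94.7-95.0% for covariate-adjusted proportions.

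**A random intercept alone.** For four oncologists with 12 patients each (REML, variance truncated at zero, 400,000 replicates), normal inference covers 95.0%, 94.1%, 91.9%, 89.1% and 85.6% at ICC 0.01, 0.02, 0.05, 0.10 and 0.20. On 2 df the same model covers 99.0% to 99.99%, with mean half-widths of 1.44 to 2.05 SD. Neither version is interchangeable with the oncologist-level comparison.

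**The case against.** The strongest reply is that the absence of an oncologist term is inferred from silence. Sections 3.1 and 8.3.1 both introduce the hierarchical model without naming an outcome, and the last sentence may only distinguish continuous from binary outcomes within that framework. The text does not exclude this. But Section 8.3.1 attaches the hierarchical estimate to prognostic understanding and then names a different method for the rest. The single-level reading is the natural one, and under either reading the sentence needs an edit.

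Four further points bear on weight:

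- **Planning use.** Sections 3.1 and 8.3.1 tie planning of the larger trial specifically to prognostic understanding, and no secondary interval is given a planning role. This stands, and it limits the harm to descriptive precision in a pilot.
- **Late quality-of-life assessments.** Section 3.1 expects nearly half the patients to die within 4 months. If 6 per oncologist remain, coverage is about 94.5%, 91.8%, 88.7% and 82.3% at the four ICCs: a smaller loss, but still material at the higher values. Post-Scan 1 and chart outcomes are not affected in this way.
- **Binary ICC scale.** The logistic figures in the table use a beta-binomial ICC. With a latent-scale ICC and covariate adjustment, coverage at a 50% event rate is 94.3%, 90.5%, 85.7% and 77.0%. The two scales are not comparable; the direction is the same.
- **Remedy.** Comparing proportions changes the effect measure from an odds ratio to a risk difference, and secondary outcomes could end up with stricter inference than the primary. Both points stand. The new text should name the effect measure, and the basis for the primary model's interval should also be stated.

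**Conclusion.** The concern holds. As written, Section 8.3.1 specifies models for secondary and exploratory outcomes that ignore the unit of randomisation. Nominal 95% intervals would cover about 94% at an ICC of 0.01, 88% at 0.05, 81% at 0.10 and 70% at 0.20, for continuous and binary outcomes alike to within about 3 points.

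These sizes assume 12-13 patients per oncologist and the ICC values shown; the true ICC is unknown and may differ by outcome. If it is negligible, there is no problem, but nothing in the documents supports assuming so for outcomes that depend on an oncologist's own practice. The section should be corrected before analysis. It does not threaten the design or conduct of the pilot.

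**What to change.** Replace the last sentence of Section 8.3.1 with:

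> Effects on secondary and exploratory outcomes will be estimated by comparing oncologist-level means (mean difference) or proportions (risk difference), after patient-level adjustment for the planned baseline covariates without the arm term, with confidence intervals on 2 degrees of freedom (4 oncologists minus 2 arms). Results will also be shown by oncologist.

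Any random-intercept linear or logistic model reported alongside should be labelled supportive. If the general statement in Section 3.1 was meant to cover these outcomes, Section 8.3.1 should say so and state the basis for the intervals. The minimum alternative is to keep the single-level models and label their intervals descriptive and not adjusted for clustering; that discloses the problem without correcting it.

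The cost is one sentence, minor programming and much wider intervals:

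- **Continuous outcome:** the half-width rises from 0.56 to 1.14 SD at ICC 0.01 (1.14/0.56 = 2.0 times) and from 0.54 to 1.96 SD at ICC 0.20 (1.96/0.537 = 3.7 times).
- **Binary outcome at 50%:** the risk-difference half-width rises from 0.27 to 0.57 at ICC 0.01 and from 0.26 to about 1.0 at ICC 0.20, so binary results will be mainly descriptive.
- **Adjustment without the arm term:** the estimate shrinks by about 2% per covariate (a true 0.80 SD is estimated as 0.78), with coverage still at 95%. This assumes the covariate is not itself clustered by oncologist.

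The change corrects the stated uncertainty. It cannot remove the influence of a single oncologist on the point estimate, which is why results by oncologist should be shown.
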